3.4 MULTIPLICITY ISSUES

Not applicable.

3.5 SAFETY ANALYSES

All safety analyses will be performed on the safety population as defined in [Section 2](#), unless otherwise specified, using the following common rules:

- The analysis of the safety variables will be essentially descriptive, and no testing is planned.
- Safety data in participants who do not belong to the safety population (eg, exposed but not enrolled) will be provided.

3.5.1 Extent of exposure

The extent of IMP exposure will be assessed by the duration of IMP exposure and compliance and summarized within the safety population. In addition, summaries will be provided by trial impact (disruption) due to COVID-19 if applicable.

Duration of IMP exposure

Duration of IMP exposure is defined as last IMP administration date – first IMP administration date +14 days (+28 days for children <30 kg), regardless of unplanned intermittent discontinuations. If the date of the last dose of IMP is missing, the duration of IMP will be left as missing.

Duration of IMP exposure (in weeks) will be summarized quantitatively and categorically:

- >0 and \leq 2 weeks
- >2 and \leq 4 weeks
- >4 and \leq 6 weeks
- >6 and \leq 8 weeks
- >8 and \leq 10 weeks
- >10 and \leq 12 weeks
- >12 and \leq 14 weeks
- >14 and \leq 16 weeks
- >16 and \leq 18 weeks
- >18 and \leq 20 weeks
- >20 and \leq 22 weeks
- >22 and \leq 24 weeks
- >24 weeks

Treatment compliance

A given administration will be considered noncompliant if the participant did not receive the number of administrations as required by the protocol.

Percentage of treatment compliance for a participant will be defined as the number of administrations that the participant was compliant divided by the total number of administrations that the participant was planned to take from the first administration of IMP up to the actual last administration of IMP.

Treatment compliance will be summarized quantitatively and categorically: <80%, \geq 80%.

3.5.2 Adverse events

General common rules for adverse events

All adverse events (AEs) will be coded to a lower-level term (LLT), preferred term (PT), high-level term (HLT), high-level group term (HLGT), and associated primary system organ class (SOC) using the Medical Dictionary for Regulatory Activities (MedDRA) version currently in effect at Sanofi at the time of database lock.

The AEs will be analyzed in the following 3 categories:

- Pre-treatment AEs: AEs that developed, worsened, or became serious during the pre-treatment period.
- TEAEs: AEs that developed, worsened, or became serious during the treatment-emergent period.
- Post-treatment AEs: AEs that developed, worsened, or became serious during the post-treatment period.

The primary AE analyses will be on TEAEs. Pre-treatment and post-treatment AEs will be described separately.

An AE with incomplete or missing date/time of onset (occurrence, worsening, or becoming serious) will be classified as a TEAE unless there is definitive information to determine it is a pre-treatment or a post-treatment AE.

If the assessment of the relationship to IMP is missing for an AE, this AE will be assumed as related to IMP. Missing severity will be left as missing.

Multiple occurrences of the same event in the same participant will be counted only once in the tables within a treatment phase.

The AE tables will be sorted as indicated in [Table 6](#).

Table 6 - Sorting of AE tables

AE presentation	Sorting rules
SOC and PT	By the internationally agreed SOC order and decreasing frequency of PTs ^{a,b}
PT	By decreasing frequency of PTs ^a

^a Sorting will be based on the overall incidence

^b The table of all TEAEs presented by primary SOC and PT will define the presentation order for all other tables (eg, treatment-emergent SAE) presented by SOC and PT, unless otherwise specified.

Analysis of all adverse events

Adverse event incidence tables will be provided for all types of TEAEs: all TEAEs, all treatment emergent Adverse Event of Special Interest (see [Table 8](#)), all treatment emergent SAEs and all TEAEs leading to permanent treatment discontinuation.

The AE summaries will be generated with number (%) of participants experiencing at least 1 event.

The overview of TEAE with the details below will be generated:

- Any TEAE
- Any treatment-emergent SAE
- TEAE leading to death
- Any treatment emergent AESI
- Any treatment emergent other AE grouping
- Any TEAE leading to permanent intervention discontinuation
- Any treatment-related TEAE

The AE summaries of [Table 7](#) will be generated with number (%) of participants experiencing at least one event.

Table 7 - Analyses of adverse events

Type of AE	MedDRA levels
All TEAE	Primary SOC and PT
TEAE related to SAR231893 as per Investigator's judgment	Primary SOC and PT
Treatment emergent SAE	Primary SOC and PT
TEAE leading to permanent study intervention discontinuation	Primary SOC and PT
Treatment emergent AESI	Primary SOC and PT
TEAE leading to death ^a	Primary SOC and PT
Pretreatment AE	Primary SOC and PT
Post-treatment AE	Primary SOC and PT

^a Death as an outcome of the AE as reported by the Investigator in the AE page.

Analysis of deaths

In addition to the analyses of deaths included in [Table 7](#) the number (%) of participants in the following categories will be provided:

- Deaths during the treatment-emergent and post-treatment periods by primary cause of death.
- Deaths in non-enrolled participants or enrolled but not treated participants.

Analysis of adverse events of special interest (AESIs) and other AEs of interest

Adverse events of special interest (AESIs) and other AEs of interest will be selected for analyses as indicated in [Table 8](#). Number (%) of participants experiencing at least one event will be provided for each event of interest.

Table 8 - Selections for AESIs and other AEs of interest

AE Grouping	Criteria
AESI	
Anaphylactic reaction	Anaphylactic reaction algorithmic approach (Introductory Guide for Standardised MedDRA Queries (SMQs) Version 18.1): includes anaphylactic reaction narrow SMQ (20000021) terms and programmatic identification of cases based on occurrence of at least two preferred terms meeting the algorithm criteria occurring within 24 hours of each other. The latter cases identified using the algorithm will undergo blinded medical review taking into account the timing of events relative to each other and to IMP administration for final determination of an anaphylactic reaction or not.
Systemic hypersensitivity reactions	SMQ [20000214] hypersensitivity narrow search and [AE corrective treatment/therapy = 'Y' or Action taken with IMP = 'Drug withdrawn' or Action taken with IMP = 'Drug interrupted'] followed by blinded medical review (documented process) for selection of relevant systemic hypersensitivity events.
Helminthic infections	CMQ10544 based on HLGT as "Helminthic disorder".
Any severe type of conjunctivitis	CMQ10498 based on PTs (See Section 5.7 ^a) and "Severe" ticked in Adverse Events eCRF page.
Any severe type of blepharitis	CMQ10497 based on HLT as "Lid, lash and lacrimal infections, irritations and inflammations" and "Severe" ticked in Adverse Events eCRF page.
Keratitis	CMQ10642 based on the following PTs [keratitis, allergic keratitis, ulcerative keratitis, atopic keratoconjunctivitis, herpes ophthalmic, ophthalmic herpes simplex, corneal infection] ^a .
Clinically symptomatic eosinophilia (or eosinophilia associated with clinical symptoms)	CMQ10641 (based on HLT = Eosinophilic disorders or PT = Eosinophil count increased) and AESI is "Yes".
Pregnancy of a female patients entered in a study as well as pregnancy occurring in a female partner of a male patient entered in a study with IMP/NIMP	"Pregnancy" or "Partner Pregnancy" checked on the Pregnancy eCRF page as reported by the investigator.
Significant ALT elevation	ALT >5 × ULN in participants with baseline ALT ≤2 × ULN; OR ALT >8 × ULN if baseline ALT >2 × ULN.
Symptomatic overdose with IMP	Symptomatic Overdose is answered Yes, with Overdose of IMP answered Yes on AE eCRF.
Symptomatic overdose with NIMP	Symptomatic Overdose is answered Yes, with Overdose of NIMP answered Yes on AE eCRF.
Other selected AE Grouping	
Serious injection site reactions or severe injection site reactions that last longer than 24 hours	HLT = 'Injection site reactions' and either with serious status, or with severe status and (AE end date/time - AE start date/time) ≥24 hours or ongoing.
Severe or serious infection	Primary SOC = 'Infections and infestations' and with severe or serious status.
Drug-related hepatic disorder	SMQ [20000006] Drug-related hepatic disorders- narrow.
Injection site reaction	HLT = 'Injection site reactions'.
Malignancy	SMQ [20000091]- Malignant or unspecified tumors narrow.
Conjunctivitis (narrow)	CMQ10644 based on the following PTs [Conjunctivitis, Conjunctivitis allergic, Conjunctivitis bacterial, Conjunctivitis viral, Atopic keratoconjunctivitis] ^a .

AE Grouping	Criteria
Conjunctivitis (broad)	CMQ10645 based on the following PTs [Conjunctivitis, Conjunctivitis allergic, Conjunctivitis bacterial, Conjunctivitis viral, Atopic keratoconjunctivitis, Blepharitis, Dry eye, Eye irritation, Eye pruritus, Lacrimation increased, Eye discharge, Foreign body sensation in eyes, Photophobia, Xerophthalmia, Ocular hyperaemia, Conjunctival hyperaemia] ^a .
Conjunctivitis (FDA)	CMQ10643 based on the following PTs [Conjunctivitis, Conjunctivitis allergic, Conjunctivitis bacterial, Conjunctivitis viral, Eye irritation, Eye inflammation, Giant papillary conjunctivitis] ^a .
Keratitis (FDA)	CMQ30102 based on the following PTs [keratitis, allergic keratitis, ulcerative keratitis, atopic keratoconjunctivitis, ophthalmic herpes simplex] ^a .

^a The list of terms may be adjusted according to MedDRA version changes

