2.3.1 Risk assessment

No tissue targets or specific hazards to humans were identified in nonclinical general and reproductive toxicology studies.

Dupilumab has an extensive safety database including in pediatric patients aged ≥ 6 months to <18 years. As of 28 March 2022, 13 577 participants were enrolled into the development program for dupilumab and included in the safety population with 311 participants with urticaria. Updated data are available in the current Investigator's Brochure.

Based on information retrieved from the Margin Consolidated (MARCO) application used by the Marketing Authorisation Holder for reporting of sales data from postmarketing experience the cumulative exposure to dupilumab parenteral formulation could be estimated to be 522 786 Patient Years for the period from 01 March 2017 through 30 September 2021.

Dupilumab has been generally well tolerated in all populations tested in clinical development programs consistent with a positive benefit/risk profile. In CSU (EFC16461) Study A, all dose regimens of dupilumab used (300 mg Q2W and 200 mg Q2W) were well-tolerated with an acceptable safety profile up to 24 weeks of study intervention.

The adverse drug reactions (ADRs) identified to date for dupilumab include injection site reactions, conjunctivitis (including allergic and bacterial), oral herpes, herpes simplex (primarily mucocutaneous in nature), blepharitis, dry eye, eye pruritus, eosinophilia, serum sickness, angioedema, arthralgia, facial rash, and keratitis (including ulcerative). These ADRs were generally mild or moderate, transient, and manageable. These ADRs were not consistently observed in all indications (see IB for greater details). More significant serious allergic reactions were very rare. Importantly, no increased overall infection risk was observed in patients treated with dupilumab.

Systemic hypersensitivity is an important identified risk for dupilumab. Therapeutic proteins and monoclonal antibodies such as dupilumab are potentially immunogenic. Hypersensitivity reactions, including generalized urticaria, rash, erythema nodosum and serum sickness, serum sickness-like reactions or angioedema, were reported in less than 1% of participants who received dupilumab in clinical trials.

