8.3.6 Disease-related events and/or disease-related outcomes not qualifying as AEs or SAEs

Signs/symptoms should be reported as an AE or SAE only if judged by the Investigator to have unexpectedly worsened in severity and/or frequency or change in nature any time during the study. If the participant has a preexisting medical history of angioedema and this condition worsens during the study, it should be reported as an AE or SAE. Any new onset of angioedema in the participant with no prior occurrence should also be reported as an AE or SAE.

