8.3.7 Adverse events of special interest

An AESI is an AE (serious or nonserious) of scientific and medical concern specific to the Sponsor's product or program, for which ongoing monitoring and immediate notification by the Investigator to the Sponsor is required. Such events may require further investigation in order to characterize and understand them. Adverse events of special interest may be added, modified, or removed during a study by protocol amendment.

- Anaphylactic reactions.
- Systemic hypersensitivity reactions.
- Helminthic infections.
- Any severe type of conjunctivitis or blepharitis.
- Keratitis.
- Clinically symptomatic eosinophilia (or eosinophilia associated with clinical symptoms).
- Increase in ALT
 - ALT $>5 \times$ ULN in participants with baseline ALT $\leq 2 \times$ ULN,
Or
 - ALT $>8 \times$ ULN if baseline ALT $>2 \times$ ULN.
- Pregnancy of a female participant entered in a study with IMP:
 - Pregnancy occurring in a female participant entered in the clinical trial. It will be qualified as an SAE only if it fulfills 1 of the seriousness criteria (see Appendix 3 [Section 10.3]),
 - In the event of pregnancy in a female participant, IMP should be discontinued,
 - Follow-up of the pregnancy in a female participant is mandatory until the outcome has been determined (See [Section 8.3.5](#)).

- Symptomatic overdose (serious or nonserious) with IMP/noninvestigational medicinal product (NIMP):
 - An overdose (accidental or intentional) with the IMP is an event suspected by the Investigator or spontaneously notified by the participant and defined as IMP greater than twice the intended dose during an interval of less than 11 (for Q2W)/25 (for Q4W) days. The circumstances (ie, accidental or intentional) should be clearly specified in the eCRF,
 - An overdose (accidental or intentional) with the NIMP is an event suspected by the Investigator or spontaneously notified by the participant and defined as at least twice the maximum prescribed daily dose, within the intended therapeutic interval.

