3.6.1.1.1 Association of Immunogenicity with Exposure, Safety and Efficacy

The safety and efficacy analysis mentioned below will be conducted using the following categories:

- ADA positive participants: Participants with treatment-emergent or treatment-boosted response.
- ADA negative participants: Participants with pre-existing immunoreactivity or negative in the ADA assay at all time points.

Impact of ADA on PK profile

Potential associations between ADA variables (eg, ADA peak titers, neutralizing antibody status, treatment-emergent, persistent, indeterminate and transient response, treatment-boosted) and impact on serum concentration profile of dupilumab may be explored. Plot of serum concentration of functional dupilumab versus visit will be provided by ADA variables for each dupilumab dose group. Individual participant plots of dupilumab concentration according to ADA status will be provided.

Impact of ADA on clinical efficacy endpoints

Associations between the ADA variables (eg, ADA peak titers, neutralizing antibody status, treatment-emergent, persistent, treatment-boosted) and the efficacy endpoints may be explored.

Association of ADA with clinical safety endpoints

Association of safety versus ADA status may be analyzed in the ADA population. The safety assessment may focus on the following events:

- Severe injection site reactions last longer than 24 hours or serious injection site reactions,
- Hypersensitivity reactions (SMQ (20000214) hypersensitivity narrow search confirmed by medical review),
- Anaphylactic reactions (SMQ (20000021) anaphylactic reaction narrow search).

Associations between ADA variables (eg, ADA peak titers, neutralizing antibody status, treatment-emergent, persistent and treatment-boosted) and safety may be explored.

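### SAP Table 8 counts systemic hypersensitivity as an AESI only if it was treated or dosing was stopped or interrupted, a condition the protocol does not set; the optional ADA analysis also leaves out algorithm-identified anaphylaxis

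*SAP*

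**What the plan says.** **Protocol.** Section 8.3.7 opens with a general rule: "An AESI is an AE (serious or nonserious) of scientific and medical concern specific to the Sponsor's product or program". Its list then contains "Systemic hypersensitivity reactions", with no condition on treatment, action taken with study drug, relatedness or severity. Section 2.3.1 states that "Systemic hypersensitivity is an important identified risk for dupilumab". Section 9.2.3.1 provides for AESI incidence tables and lets AESIs be defined by preferred term or by a grouping fixed in advance.

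**SAP 3.5.2, Table 8.** Systemic hypersensitivity is selected by "SMQ [20000214] hypersensitivity narrow search and [AE corrective treatment/therapy = 'Y' or Action taken with IMP = 'Drug withdrawn", with drug interruption as the last alternative. Medical review then picks the relevant systemic events. Anaphylaxis is selected by narrow SMQ terms plus "programmatic identification of cases based on occurrence of at least two preferred terms meeting the algorithm criteria occurring within 24 hours of each other"; these algorithm cases go to medical review. The overview line for any AESI and the AESI row of Table 7 rest on the Table 8 selections.

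**SAP 3.6.1.1.1, association of ADA with safety.** This analysis is optional. It names "Hypersensitivity reactions (SMQ (20000214) hypersensitivity narrow search confirmed by medical review") and "Anaphylactic reactions (SMQ (20000021) anaphylactic reaction narrow search"). The first has no treatment or dosing filter. The second has no algorithm cases.

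**SAP 3.8, changes to protocol-planned analyses.** The section lists the change from exposed to enrolled participants in the population definitions and the longer treatment-emergent period for children under 30 kg. It does not mention a narrower AESI selection.

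**The concern.** The SAP selection is narrower than the protocol category it is meant to summarise, and the narrowing comes before the clinical judgement. The reviewer sees only events that were treated or that led to withdrawal or interruption. An untreated reaction with no action on study drug is therefore left out by a data filter, even if the site flagged it as an AESI and notified the sponsor under protocol 8.3.1.

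At stake is whether the AESI rows for an important identified risk agree with what the sites reported. With so few children, one case decides whether the row shows zero.

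The anaphylaxis definitions raise a second issue of consistency. The ADA analysis could omit a child whom Table 8 counts as having had anaphylaxis, with no reason given.

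**Working it through.** The plan states no figure on this point, so the check is mainly a comparison of definitions.

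**1. Does the protocol mean treated reactions only?** It does restrict to treated, drug-related reactions in two other places: the permanent discontinuation rule in 7.1.1, and the trigger for extra PK and ADA samples in footnote r of the schedule of activities (1.3). The footnote words these reactions as a kind of AESI, that is, as a subset. The AESI definition in 8.3.7 is therefore the wider one.

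**2. Systemic hypersensitivity.** Take an event that is coded in narrow SMQ 20000214 and that a medical reviewer would confirm as systemic. Run it through the three definitions:

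| Treated? | Action on study drug | Protocol 8.3.7 AESI | SAP Table 8 | SAP 3.6.1.1.1 |
|---|---|---|---|---|
| No | None | Yes | **No** | Yes |
| No | Withdrawn | Yes | Yes | Yes |
| No | Interrupted | Yes | Yes | Yes |
| Yes | None | Yes | Yes | Yes |
| Yes | Withdrawn | Yes | Yes | Yes |
| Yes | Interrupted | Yes | Yes | Yes |

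Five of the six combinations agree. Only the untreated reaction with no action on study drug differs.

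**3. Where that case is still reported.** It is missing from the Table 8 count, the Table 7 AESI row and the AESI line of the overview. It remains in the all-TEAE table by SOC and PT, in the related-TEAE table if judged related, and in the SAE table if serious.

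**4. Anaphylaxis.**

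| How the case is found | SAP Table 8 | SAP 3.6.1.1.1 |
|---|---|---|
| Narrow SMQ term | Yes | Yes |
| Algorithm only, confirmed on review | Yes | **No** |
| Algorithm only, not confirmed | No | No |

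**5. Size, as an illustration.** Assume that all 15 enrolled children (SAP section 4) are in the safety population and that exactly one has an untreated systemic reaction with no action on study drug. Exact (Clopper-Pearson) 95% intervals:

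- Table 8 as written: 0/15 = 0%. The upper limit is 1 − 0.025^(1/15) = 21.8%, so the interval is 0 to 21.8%.
- With the case admitted: 1/15 = 6.7%. The lower limit is 1 − 0.975^(1/15) = 0.2%. The upper limit is the 0.975 quantile of Beta(2, 14), 31.9%.

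The documents give no expected number of such cases.

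**The case against.** The strongest defence is that 8.3.7 governs what sites must notify, while 9.2.3.1 lets the analysis use a grouping fixed in advance. A search-based selection is therefore legitimate, and the event is still reported to the sponsor and still tabulated as a TEAE. This stands as far as it goes. It does not explain why the grouping should be narrower than the protocol category, or why SAP 3.8 is silent about it.

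The expected yield is also small. Protocol 2.3.1 puts hypersensitivity reactions at under 1% of dupilumab-treated trial participants. If that rate applied here, 15 × 0.01 = 0.15 cases would be an upper bound, and untreated cases would be fewer still. That argues for a modest priority.

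On the ADA analysis, 3.6.1.1.1 is optional and its hypersensitivity item is not limited to systemic reactions, so a broader set there may be intended. That stands too. Only the anaphylaxis difference is a clear mismatch.

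A reader might infer more than the documents support:

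- *Treated CSU flares pass the filter, so it selects the wrong events.* Passing the filter is not being counted; the medical review that follows can remove flares.
- *The two-term algorithm fails because habitual hives go unrecorded.* Protocol 8.3.6 does say "Signs/symptoms should be reported as an AE or SAE only if judged by the Investigator to have unexpectedly worsened in severity and/or frequency", but the sentence goes on to include a change in nature, and new or worsened angioedema must be reported. Protocol 10.3.3 asks for the diagnosis rather than separate signs where possible, so a recognised anaphylaxis should not depend on the algorithm.
- *The eosinophilia row is a precedent for the change.* There the AESI flag is joined by AND and restricts the search. It shows only that the flag exists.

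**Conclusion.** The point holds in limited form. Table 8 applies a treatment-or-dosing condition that protocol 8.3.7 does not contain and that SAP 3.8 does not declare. One class of site-reported AESI, untreated with no action on study drug, is thereby kept from review and left out of the AESI rows. Separately, algorithm-only anaphylaxis confirmed in Table 8 would be missing from the ADA-safety analysis if that analysis is done.

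It would be wrong to infer that these reactions vanish from the report, because the TEAE tables retain them. It would also be wrong to infer that a case has been lost, because the documents hold no outcome data. The change from 0/15 to 1/15 (6.7%) rests on one hypothetical case and on all 15 children being in the safety population. Percentages by the two weight groups would not match the planned output, since SAP 3.1 reports overall and by four intervention groups.

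This is a correction to a stated selection rule in a descriptive safety analysis. It is worth making because it is nearly free and concerns an important identified risk.

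**What to change.** 1. **Table 8, systemic hypersensitivity.** Select narrow SMQ 20000214 and [corrective treatment, or drug withdrawn, or drug interrupted, or investigator AESI = Yes], followed by the planned medical review. Keep the present selection as a second row, so that counts remain comparable with the existing definition.
2. **SAP 3.6.1.1.1.** Use the Table 8 anaphylaxis case set, including confirmed algorithm cases. For hypersensitivity, either use the reviewed Table 8 systemic set or keep the unfiltered item and label it as deliberately broader.
3. **SAP 3.8.** Record the change from the protocol category and the reason for the selection adopted.

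The cost is SAP wording, one more selection condition and a few more events for review. It assumes that the AESI flag used in the eosinophilia row is also recorded for hypersensitivity events. Flagged events coded outside the narrow SMQ, and untreated events that the site did not flag, would still not enter. That is a consequence of keeping a search-based grouping, which protocol 9.2.3.1 allows. No protocol amendment or new data collection is needed.
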